**Effect of acceptance and commitment therapy
on stigma in college students with irritable
bowel syndrome: a randomized controlled study**

October 18, 2022

Study Protocol

1. Integrity Statement

(1) Ensure that the operation is in strict accordance with the test protocol and the authenticity of the data records; (2) No conflict of interest with other projects.

2. Title of the study

Effect of acceptance and commitment therapy on stigma in college students with irritable bowel syndrome: a randomized controlled study

3. Flow chart of the implementation of the study

Specific implementation contents of the intervention programme

Module topics	Module objectives	Intervention contents	Homework
Week 1 Building relationships understanding ACT	Understanding the ACT content	
 1. The researcher and the patient introduce themselves, get to know each other and establish a good relationship. (5 minutes) 2. Understand the patient's psychological state and encourage each patient to tell their experience of IBS, their views on IBS and their knowledge of IBS health. (10 minutes) 3. Introduce the six core components of ACT and the treatment process, and explain the application of ACT to help patients realize that they can improve their current psychological state and enhance their confidence through intervention. (15 minutes) 4. Teach patients to mindfulness breathing. (10 minutes) 5. Live answer: answer patients' questions and start a discussion. (10 minutes) 	Perform Positive Exercises 1-2 per day and record a video to upload to WeChat group.
Week 2 Acceptance of disease	Positive acceptance Abandon confrontation	
 1. Live discussion: encourage patients to express their thoughts, describe the reasons for their worries or fears, their inner feelings, etc., after experiencing the disease, and share the measures taken to cope with these thoughts or feelings and their effects. (10 minutes) 2. Live video broadcast: explain the metaphor of "Tug-of-War with Monsters" to convey to patients that in difficult situations, the more they struggle, the worse the situation will be, and to promote the acceptance of negative emotions by patients, and to correctly face the disease and pain. "Struggle Switch": give up the struggle against physical and emotional pain and accept the true feelings. (20 minutes) 	Patients are encouraged to keep a diary every day, take photos and upload them to email to exchange ideas with researchers. Record your struggles with painful thoughts or emotions and think about how cognitive dissociation strategies should be used to regulate emotions.

(Continued)

Module topics	Module objectives	Intervention contents	Homework
		
3. Establish correct knowledge of IBS and acceptance of IBS. Tell patients to face painful experiences with an open attitude of acceptance, avoidance will only deepen the bondage of suffering. (10 minutes)
 
4. Live answer: answer patients' questions and start a discussion. (10 minutes)
	
Week 3	Reducing the problematic dominance of patient cognition over behavior	
1. Explaining to patients the importance of rationally coping with negative emotions, carrying out cognitive dissociation exercises, helping patients to identify "thoughts" and "reality", and making patients realize that "thoughts" are not "facts per se", and guiding patients to normalize their painful emotions by separating negative thoughts from reality. (10 minutes)
 
2. Live video: "I am having this thought" exercise to reduce or get rid of emotional pain. (20 minutes)
 
3. Use the metaphor of "leaves floating down the stream" to help patients separate the ideal from the reality, so that they can learn to look at the stigma of IBS from an observer's point of view with a more relaxed mindset, and not to get caught up in it. (10 minutes)
 
4. Live answer: answer patients' questions and start a discussion. (10 minutes)
	
Practice "Leaves Floating in the Stream" every day, write down your own experience, take photos and upload them to email to exchange ideas with researchers.

Week 4	Dissociation from the conceptualized self	
1. Change the patient's concept of "self" and guide the patient to positively accept IBS. (10 minutes)
 
2. Conduct a "checkerboard metaphor" exercise to guide patients
	
Patients are guided to empty themselves, to be in the present moment, to be

(Continued)

Module topics	Module objectives	Intervention contents	Homework
		
to focus on their lives in the present, accept their own emotions, and pay attention to their true selves in the present moment. (20 minutes)
 
 Facilitate self-expression without being held back by conceptualizations of self or others. (10 minutes) Live discussion: think about the changes brought about by IBS and guide patients to practice body scanning. (10 minutes) 	
consciously aware of their thoughts, to think about the changes brought about by the illness, and to record them.

Week 5	Focus on your core values	
 Introduce the values in ACT, use interviews with IBS patients to help them clarify their values, guide them to identify "what is most important to them", and develop a list of goals based on their own values and use them as goals and directions for action. (10 minutes) Picture display: using the metaphor of "Donkey, Stick and Carrot" to introduce values. (10 minutes) Compass Metaphor: work with the patient to understand the importance of values and to guide patients to develop confidence in improving levels based on their own values. (20 minutes) Live answer: answer patients' questions and start a discussion. (10 minutes) 	
Write out their own value goals, reflect on the values, and share ideas with the researcher and peers during the next intervention session.

Week 6	Guided by values toward a meaningful life	
 Introduce the importance of commitment to action: according to their own values, guide patients to clarify "what kind of person they want to be", think about the goals they want to achieve, and consider the problems and solutions they may encounter in the process of implementation, and help them to develop a practical 	
Encourage patients to think about what they want to achieve. What is the specific process for achieving it?

(Continued)

Module topics	Module objectives	Intervention contents	Homework
		
plan together. (10 minutes)
 
2. Set SMART behavioral goals: S-Specific; M-Measurable; A-Achievable; R-Realistic; T-Time-bound. (10 minutes)3. Live discussion: summarize and review the whole process of the ACT intervention, and invite each member to share their own gains and feelings during the intervention. (10 minutes)4. Encourage each member to strengthen the use of ACT in their future study and life. (15 minutes)	

4. Background

Acceptance and commitment therapy (ACT), as a new cognitive intervention therapy, emphasizes value-oriented goal setting, which mainly includes six core processes: acceptance, cognitive dissociation, experiencing the present moment, self-as-context, clarifying values and committed action, which is conducive to solving the psychological disturbances existing in patients with chronic pain, HIV, cancer, epilepsy, irritable bowel syndrome, etc., and increasing the degree of self-acceptance and reducing the stigma of illness. Through diverse therapeutic approaches, psychological flexibility is increased and the impact of unrealistic thoughts on daily life and goal achievement is limited. There are many reports of domestic studies related to ACT on reducing the sense of shame in patients with chronic diseases, but there have been no intervention studies on ACT to reduce the sense of shame in patients with IBS, and there is a lack of applied research on systematic intervention programs. Therefore, in this study, we used ACT as the basis for developing an intervention program to reduce the stigma, and explored the effectiveness of ACT in reducing the stigma in IBS patients, with the aim of enhancing their mental health and improving their quality of life.

5. Research purpose

The purpose of this study was to construct a stigma intervention program for college students with Irritable Bowel Syndrome (IBS) based on the Acceptance and Commitment Therapy (ACT) theory and to investigate the effectiveness in reducing stigma in IBS patients with the aim of enhancing their mental health and improving their quality of life.

6. Inclusion and Exclusion Criteria

Inclusion criteria: (1) Patients with IBS who meet the Rome IV diagnostic criteria; (2) Duration of IBS disease \geq 0.5 years; (3) The Perceived Stigma Scale in IBS (PSS-IBS) total score \geq 80; (4) Patients can proficiently use WeChat and participate in remote follow-ups; (5) Understand the research content, participate voluntarily and sign the

informed consent. Exclusion Criteria: (1)Patients with other intestinal diseases or serious primary diseases; (2) Patients with comorbid psychiatric diseases; (3) Patients who engaged in psychological workers or received psychological counseling within 3 months; (4) Patients who have recently participated in or are currently participating in other similar studies.

7. Intervention process

From June 2023 to January 2024, college students with irritable bowel syndrome (IBS) accompanied by a sense of shame who met the inclusion and exclusion criteria were selected from a comprehensive university in Yangzhou City. The control group implemented conventional health education on IBS, and the intervention group implemented psychological intervention program based on ACT theory on top of the control group.

8. Sample size estimation

The required sample size was calculated by comparing the means of the two samples, applying the following formula: $n=2[(Z\alpha/2+Z\beta)\sigma/\delta]^2$, the test level was taken as two-sided $\alpha=0.05$ and $\beta=0.10$, which resulted in $\mu\alpha=1.96$, and $\mu\beta=1.282$, the two-sided test was used, reviewing the literature, $\sigma=5.15$ and $\delta=4.01$, the calculation was made that $n1=n2=35$ cases, and the 20% loss of visit rate was considered. Finally, there were 42 cases in each group, and the total sample size was 84 cases. In the process of the study, there were 2 cases of lost visits in the control group, of which 1 case withdrew in the middle of the study and 1 case was interrupted; there were 2 cases of lost visits in the intervention group, of which 1 patient withdrew due to aggravation of the disease and 1 case was interrupted, and the final sample size included in the statistical analysis was 80 cases, with 40 cases in each group.

9. Randomisation

Participants were identified through related questionnaire survey, and participants signed a written consent form to participate in the study. After the baseline assessment, using a randomized grouping approach, patients who met the inclusion and exclusion

criteria were numbered and randomly divided into a control group and an intervention group by a computerized random number procedure.

10. Measurement index

General information questionnaire: baseline (T0); perceived stigma scale in IBS (PSS-IBS) (primary indicator): baseline (T0), 1 month post intervention (T1), 3months post intervention (T2); acceptance and action questionnaire-II (AAQ-II) (secondary indicator): baseline (T0), 1 month post intervention (T1), 3months post intervention (T2); self-acceptance questionnaire (SAQ) (secondary indicator): baseline (T0), 1 month post intervention (T1), 3months post intervention (T2); IBS quality of life (IBS-QOL) (secondary indicator): baseline (T0), 1 month post intervention (T1), 3months post intervention (T2).

11. Ethical consideration

The study was ethically approved by the Ethics Committee of the College of Nursing of Yangzhou University (YZUHL20220044).

12. Statistical analysis of data

SPSS 25.0 software was applied for data analysis. Measurement data conforming to normal distribution were described by mean \pm standard deviation, those not conforming to normal distribution were described by median (inter-quartile spacing), and count data were expressed by frequency and constitutive ratio. The t-test was used for between-group comparison of measures that met normal distribution, the Mann-Whitney U test was used for between-group comparison of measures that did not meet normal distribution, the χ^2 test was used for categorical variables, and Mauchly's test of sphericity was used, and if the covariance matrix did not satisfy the sphericity symmetry, the correction coefficient (Epsilon) was used to correct for the degrees of freedom, and the Greenhouse-Geisser was used for correcting results. Trends in PSS-IBS, AAQ-II, SAQ, and IBS-QOL scores over time were analyzed using ANOVA of repeated measures data for both study groups at pre-intervention, 1 month post-intervention, and 3 months post-intervention.

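### The 42 per group in section 8 keeps the required 35 evaluable only up to 16.7% loss, not the stated 20%; 20% would need 44 per group

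*Combined protocol and SAP*

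**What the plan says.** Section 8 (Sample size estimation) sizes the trial for a comparison of two means, with two-sided α of 0.05, β of 0.10, a standard deviation of 5.15 and a difference of 4.01, both taken from unspecified literature. From these, "the calculation was made that $n1=n2=35$ cases". It continues: "the 20% loss of visit rate was considered. Finally, there were 42 cases in each group", and "the total sample size was 84 cases". Neither section 8 nor any other section states how the loss rate was turned into 42.

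The same paragraph also reports the outcome. Two patients were lost in each group, and "the final sample size included in the statistical analysis was 80 cases, with 40 cases in each group".

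**The concern.** A loss rate is normally a share of the patients enrolled. If 20% of those enrolled are lost, the number enrolled has to be the evaluable number divided by 0.80. The 42 looks like the evaluable number multiplied by 1.20, which always gives too few.

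At stake is whether the printed justification meets its own terms. A reader would take it that 42 per group still leaves 35 evaluable, and so 90% power, when losses reach 20%. If it does not, the plan promises more protection than it has, and the figure may be carried into the trial report.

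**Working it through.** **Inputs, all from section 8:** two-sided α = 0.05 (z = 1.96); β = 0.10 (z = 1.282); σ = 5.15; δ = 4.01; loss rate 20%; 42 per group and 84 in total.

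**1. Number before losses (the plan's own formula).**

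n = 2[(1.96 + 1.282) × 5.15 / 4.01]² = 34.67, so 35 per group. The stated 35 is reproduced.

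**2. Where 42 comes from.**

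35 × 1.20 = 42 exactly. This origin is inferred from the match, because the plan does not show the step.

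**3. What 42 leaves after 20% loss.**

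- Per group: 42 × 0.80 = 33.6, against 35 needed.
- In total: 84 × 0.80 = 67.2, against 70 needed.

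**4. What 20% loss would require.**

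35 / 0.80 = 43.75, so 44 per group and 88 in total: 2 more per group, 4 more overall. Rounding does not explain the gap, since the unrounded figure gives 34.67 / 0.80 = 43.3, again 44.

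**5. The loss that 42 can absorb.**

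1 − 35/42 = 16.7%. In whole patients:

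| Lost of 42 | Share | Left |
|---|---|---|
| 7 | 16.7% | 35 |
| 8 | 19.0% | 34 |

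The eighth loss is still within the stated 20% and already takes the group below 35.

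**6. Power.**

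With d = 4.01/5.15 = 0.7786, the plan's normal approximation is power = Φ(d√(n/2) − 1.96). The two-sided t-test figures use the noncentral t distribution.

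| Evaluable per group | Normal approximation | t-test |
|---|---|---|
| 35 | 90.3% | 89.5% |
| 34 (8 of 42 lost) | 89.4% | 88.6% |
| 33.6 (20% lost) | 89.1% | 88.2% |

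From 35 to 33.6 the drop is 1.2 points (normal) or 1.3 points (t-test). The t-test value at 35 is just under 90% because the planning formula is a normal approximation. That is separate from the loss step.

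**7. What happened.**

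Reported loss was 2/42 = 4.8% per group. At the 40 per group analysed, power by the plan's formula is 93.6%.

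**The case against.** The strongest reply is that section 8 says only that a 20% loss rate was taken into account. It gives no inflation rule. If the authors meant to add 20% to the required 35, then 35, 20% and 42 agree. But the plan calls the 20% a loss rate, and the same paragraph counts its actual losses among the 42 enrolled in each group. On that basis 20% of 42 is 8.4 patients, and 35 do not remain. If a mark-up was intended, the description is still wrong and the same correction is needed.

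A second reply is that the effect is trivial, and much of this stands. The drop of 1.2 to 1.3 points is of the same order as the 0.8 points between the normal and t-test figures at 35 per group. It is also about what a slightly different σ would cost: with σ = 5.25 in place of 5.15 (an assumed value, for illustration), power by the plan's formula at 35 per group falls by about 1.1 points. The power figures also describe a simple two-group comparison, while section 12 also plans repeated-measures ANOVA over three time points. They show the size of the slip on the plan's own formula and should not be read as the power of that analysis.

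Third, losses were low and no enrolment decision remains open. That also stands. It limits the point to the printed justification.

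**Conclusion.** The concern holds as a minor arithmetic error. The stated 42 per group does not keep 35 evaluable, or meet β = 0.10 by the plan's own formula, at the plan's own 20% loss rate. It covers 16.7%. The shortfall against 44 is 2 per group, or 4 in total.

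This rests on reading the loss rate as a share of those enrolled, and on taking the plan's σ and δ as given. That 42 came from 35 × 1.20 is an inference, but the conclusion does not depend on it: 42 falls short at 20% loss however it was reached. The achieved sample was not harmed, since 40 per group were analysed against 35 required. The point is not evidence that the trial was underpowered.

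**What to change.** Replace the loss statement in section 8 with one sentence:

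> 35 evaluable per group are required; 42 enrolled per group allows for up to 16.7% loss (7 of 42); at 20% loss, power by the same formula would be about 89%.

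This keeps the 20% case in view. If the sponsor can confirm that 42 was obtained as 35 × 1.20, the text should say so.

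The cost is one sentence, with no extra enrolment and no change to the analysis. What is given up is the claim to a 20% allowance: the stated figure becomes 16.7%.

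### PSS-IBS is the only primary indicator, but the plan does not name the visit or the repeated-measures ANOVA effect that decides the trial

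*Combined protocol and SAP*

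**What the plan says.** - Section 10 (Measurement index) gives "perceived stigma scale in IBS (PSS-IBS) (primary indicator): baseline (T0), 1 month post intervention (T1), 3months post intervention (T2". AAQ-II, SAQ and IBS-QOL are each marked secondary. No visit is singled out for any scale.
- Section 12 (Statistical analysis of data) names one procedure for the primary scale, in a sentence it shares with the three secondary scales: "Trends in PSS-IBS, AAQ-II, SAQ, and IBS-QOL scores over time were analyzed using ANOVA of repeated measures data for both study groups". A Greenhouse-Geisser correction applies if sphericity fails. No effect (group, time or group-by-time) is named as the one to be judged.
- The same section says "The t-test was used for between-group comparison of measures that met normal distribution", with Mann-Whitney U as the non-normal alternative. That sentence is tied to no scale and no visit.
- Section 8 (Sample size estimation) says "The required sample size was calculated by comparing the means of the two samples", at two-sided 0.05. It names neither scale nor visit. It also reports that "the final sample size included in the statistical analysis was 80 cases", 40 per group.
- No section gives a success criterion or a rule for combining several PSS-IBS results.

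**The concern.** A primary scale is not yet a primary test. A repeated-measures ANOVA with two groups and three visits yields three F tests. The unassigned t-test sentence could add a comparison at T1 and another at T2. If none of these is named in advance, more than one could be put forward as the trial's answer.

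The candidates also answer different questions:
- The group main effect averages the difference over all three visits, including T0, where randomised groups should be alike. That dilutes a real effect.
- The group-by-time effect asks whether the two groups change differently.
- The time effect does not compare the groups at all. Entry requires a PSS-IBS total of at least 80, so scores may fall in both groups whatever ACT does.
- A single-visit t-test matches the form of the sample size calculation but ignores T0.

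Which test is called primary can therefore decide whether the trial is called positive.

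**Working it through.** **Inputs from section 8.** Sigma 5.15, delta 4.01, two-sided alpha 0.05, beta 0.10, 40 analysed per group.

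**Assumptions, not in the plan.** Sigma and delta refer to PSS-IBS; normal data; equal SDs; the same correlation r between any two visits, taken from 0.2 to 0.8; the full effect at both T1 and T2 unless stated.

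**Step 1: the plan's own figure.** 2[(1.96 + 1.282) × 5.15/4.01]² = 34.7, so 35 per group reproduces. This is the size for one comparison of two means. The standardised effect is d = 4.01/5.15 = 0.779. With 40 per group one t-test at 0.05 has 93.0% power (exact noncentral t).

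**Step 2: false-positive rate when no test is named.** Under these assumptions the group and group-by-time tests are independent, so the chance that at least one is significant under no effect is 1 − 0.95² = 9.75%. Simulation with the Greenhouse-Geisser correction (100,000 trials per value of r) gives, counting significance in either direction:

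| Result that may count | r = 0.2 | r = 0.8 |
|---|---|---|
| Group or group-by-time | 9.6% | 9.6% |
| t-test at T1 or at T2 | 9.6% | 7.9% |
| Any of these four | 14.3% | 12.4% |
| Any one named test | about 5% | about 5% |

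If only results favouring ACT count, the first three rows become about 5%, 5% to 4%, and 7.5% to 6%, against 2.5% for one named test. The relative inflation is about the same.

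**Step 3: power of each candidate at 40 per group.**

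- *Group main effect.* Standardised effect (2/3)d/√((1 + 2r)/3), times √20 for the noncentrality. At r = 0.2: 0.519/0.683 = 0.760, times √20 = 3.40, power 92%. At r = 0.8: 0.519/0.931 = 0.558, times √20 = 2.49, power 69%.
- *Group-by-time.* The centred effects (−2/3, 1/3, 1/3)d have squares summing to (2/3)d², so the noncentrality is 20 × (2/3) × 0.779²/(1 − r): 10.1 at r = 0.2 (power 81%) and 40.4 at r = 0.8 (over 99%). An effect at one visit only gives the same sum of squares, hence the same power.
- *T0-adjusted difference at one visit.* Effect d/√(1 − r²); simulated power 94% at r = 0.2, over 99% at r = 0.8.
- *T0-adjusted difference averaged over T1 and T2.* Effect d/√((1 + r)/2 − r²); simulated power over 99% throughout. If the effect is at one visit only the numerator halves, and power is about 63% (r = 0.2) to 92% (r = 0.8).
- *Two unadjusted t-tests at 0.025 each.* 88% for one particular visit. For at least one of the two, with equal effects, about 98% at r = 0.2 and 93% at r = 0.8.

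**The case against.** The strongest reply is that section 12 already points to one test. The only analysis that names PSS-IBS is a repeated-measures ANOVA of trends in both groups. The sphericity correction concerns only the within-subject effects, and of those only group-by-time compares the groups. The t-test sentence may serve the baseline table alone. Much of this stands: group-by-time is the most natural reading. It remains an inference, because the wording also fits a time effect or a separate trend in each group, and section 8 is built on a different comparison.

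It is also fair to say that the power figures rest on inputs the plan does not give. Section 8 ties its sigma and delta to no scale, and no correlation is stated. They help in choosing a test; they are not needed to show that none was named.

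Four stronger inferences are tempting and unsupported:
- *That the trial runs at 10% to 14% error.* Those rates need a rule that any significant PSS-IBS result may count, which the plan does not contain. The four-test figure is a worst case, since nothing says that t-tests at T1 and T2 were intended.
- *That those rates are for results favouring ACT.* They count both directions; the one-directional rates are about half.
- *That splitting 0.025 between T1 and T2 is underpowered.* The 88% applies only if one particular visit must succeed or the effect is confined to one visit.
- *That a result was picked after the fact.* The documents report how many cases were analysed, not what was found or when a test was chosen.

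**Conclusion.** The point holds as a gap in specification that should be closed: there is one primary scale, but no deciding visit or effect. The inflation to about 10% (group or group-by-time), 8% to 10% (T1 or T2 t-test) or at worst 12% to 14% (all four) is conditional on an any-result rule and on the working assumptions; any single named test stays at about 5%. The choice of test has consequences of its own. If section 8's sigma and delta apply to PSS-IBS with equal effects at T1 and T2, power for the group main effect falls from about 92% to 69% as the correlation rises from 0.2 to 0.8, while group-by-time rises from about 81% to over 99%. The sample size arithmetic of 35 per group before allowance for loss is not in question here.

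**What to change.** In section 12, name one primary PSS-IBS test at two-sided 0.05. The options, in order:

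1. **Preferred:** the between-group difference adjusted for the T0 score, averaged over T1 and T2 or at one named visit. It uses data already collected and has about 93% power or more under the assumptions above. Its weakness is that the average loses power if the effect is at one visit only.
2. **Acceptable, and closest to the plan:** the group-by-time effect with its Greenhouse-Geisser correction, reported with the T1 and T2 group differences and 95% confidence intervals, because a test on two degrees of freedom does not itself show direction. It is the weaker choice when the correlation is low and the effect is equal at both visits.
3. **Also acceptable:** 0.025 at each of T1 and T2, with success if either is significant.

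State what the t-test/Mann-Whitney sentence covers. Label every other PSS-IBS test, including the time effect, supportive. Because section 8 already reports the analysed cases, state whether the choice was made before or after the data were seen, and report all PSS-IBS tests. A choice made afterwards cannot be called pre-specified.

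The cost is a few sentences and no new data. The price to the sponsor is that a result significant only on a supportive test no longer counts as primary success.

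### Section 12 ties no treatment difference, model term or visit to the primary PSS-IBS outcome; adjusting the T1 and T2 group comparisons for T0 is a free improvement

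*Combined protocol and SAP*

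**What the plan says.** - Section 10 defines the outcome: "perceived stigma scale in IBS (PSS-IBS) (primary indicator): baseline (T0), 1 month post intervention (T1), 3months post intervention (T2"). Neither T1 nor T2 is named as the deciding visit.
- Section 9 places T0 before allocation: "After the baseline assessment, using a randomized grouping approach". T0 is therefore a valid covariate.
- Section 12 analyses the four scales as follows: "Trends in PSS-IBS, AAQ-II, SAQ, and IBS-QOL scores over time were analyzed using ANOVA of repeated measures data for both study groups". The visits it then lists are baseline and the two follow-ups, so T0 is one of three levels of the repeated factor, and no covariate is mentioned.
- The same section adds a Greenhouse-Geisser correction through Mauchly's "test of sphericity was used, and if the covariance matrix did not satisfy the sphericity symmetry".
- It also lists a general test: "The t-test was used for between-group comparison of measures that met normal distribution", with Mann-Whitney U for non-normal measures. No outcome, visit or adjustment is attached.
- Section 8 gives the basis of the sample size: "The required sample size was calculated by comparing the means of the two samples". It also reports that "the final sample size included in the statistical analysis was 80 cases, with 40 cases in each group".
- Section 6 requires a PSS-IBS total of at least 80 at entry, so T0 is cut off from below.

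**The concern.** A three-visit, two-group repeated-measures ANOVA gives a group, a time and a group-by-time result, and these answer different questions. Section 12 does not say which decides effectiveness. Its language of trends over time, and the sphericity correction, which concerns only within-subject terms, point to time and group-by-time.

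The time effect is not a treatment effect. Both arms were selected for high PSS-IBS and may fall without ACT. Group-by-time is a valid comparison and uses T0, but it is a test on 2 degrees of freedom and yields no single difference. The trial was sized for such a difference, and section 12 commits to none for PSS-IBS, with or without a confidence interval.

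Two things are at stake. The reader cannot tell which result settles the question. And where groups are compared at follow-up, nothing in the plan uses T0 to sharpen the comparison, although T0 is held for every patient who entered.

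**Working it through.** **Inputs.** From section 8: two-sided alpha 0.05, beta 0.10, sigma 5.15, delta 4.01, 40 analysed per group. The documents do not link 5.15 and 4.01 to PSS-IBS or to a visit; that is an assumption. They give no correlation between visits; r = 0.3 / 0.5 / 0.7 is assumed, equal between all visits, with equal SDs.

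**1. The plan's own figure.** 2[(1.96 + 1.282) × 5.15 / 4.01]² = 34.67, so 35 per group. It reproduces. At 40 per group the unadjusted SE at one visit is 5.15 × √(2/40) = 1.152, and the t-test has 93% power.

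**2. What the ANOVA terms estimate** if ACT shifts T1 and T2 by 4.01 and T0 by nothing:
- Time: change averaged over both arms, so no treatment comparison.
- Group main effect: (0 + 4.01 + 4.01)/3 = 2.67, two thirds of the effect.
- Group-by-time: valid, 2 df, no single estimate.

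**3. SE gain from T0, without regard to the entry rule.** At one visit the SE is multiplied by √(1 − r²). For the T1-T2 mean, the variance in units of sigma² falls from (1 + r)/2 to (1 + r)/2 − r².

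| | r = 0.3 | r = 0.5 | r = 0.7 |
|---|---|---|---|
| One visit: SE from 1.152 to | 1.099 (−5%) | 0.997 (−13%) | 0.822 (−29%) |
| T1-T2 mean: SE | 0.928 to 0.862 (−7%) | 0.997 to 0.814 (−18%) | 1.062 to 0.691 (−35%) |

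**4. The same with an entry cut.** The cut narrows T0 and weakens its correlation with follow-up. For illustration, suppose it keeps the top half of a normal baseline. The T0 variance is then multiplied by v = 1 − 2/π = 0.363. With V = r²v + 1 − r², the correlation of T0 with follow-up becomes r√(v/V), and that of T1 with T2 becomes (r²v + r − r²)/V. For r = 0.5: V = 0.25 × 0.363 + 0.75 = 0.841, giving 0.329 and 0.405. Follow-up SD is held at 5.15.

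| | r = 0.3 | r = 0.5 | r = 0.7 |
|---|---|---|---|
| Correlation of T0 with follow-up | 0.186 | 0.329 | 0.509 |
| One visit: SE from 1.152 to | 1.131 (−2%) | 1.088 (−6%) | 0.991 (−14%) |
| 95% CI half-width (1.991 × SE), from 2.29 to | 2.25 | 2.17 | 1.97 |
| T1-T2 mean: SE | 0.913 to 0.888 (−3%) | 0.965 to 0.888 (−8%) | 1.018 to 0.833 (−18%) |

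The percentages depend only on r and the cut; the absolute SEs also depend on 5.15.

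**5. Cost.** One degree of freedom. If r were 0, power for the T1-T2 mean at half the planned effect would go from 0.682 to 0.676.

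**6. Power by simulation**, with the cut, Greenhouse-Geisser applied, effect 4.01 at T1 (12,000 runs per cell in the first two rows, 6,000 in the last two). Entries are percentages at r = 0.3 / 0.5 / 0.7.

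| Effect at T2 | T0-adjusted T1-T2 mean | Group-by-time | T0-adjusted, T2 only |
|---|---|---|---|
| Full | 99 / 99 / 99.8 | 92 / 95 / 98 | 94 / 95 / 98 |
| Half | 91 / 91 / 94 | 79 / 86 / 94 | 41 / 44 / 51 |
| Quarter | 79 / 78 / 83 | 81 / 88 / 95 | not run |
| None | 59 / 61 / 66 | 88 / 94 / 98 | not run |

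With no effect at either visit, the adjusted mean and group-by-time both rejected in about 5% of runs.

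**7. What T0 itself contributes to power.** In a separate run with the cut and the full effect at both visits, the T1-T2 mean had 99.2 / 98.4 / 97.4% power unadjusted and 99.3 / 99.4 / 99.7% adjusted. T0 adds about 0.1 / 1.0 / 2.3 points. At r = 0.3 and 0.5, most of the lead over group-by-time therefore comes from using one averaged contrast on 1 df. With the effect halved at T2, T0 adds about 1 / 5 / 11 points.

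**The case against.** The strongest reply is that the named analysis already uses baseline. Group-by-time is valid and has 92 to 98% power for a sustained effect of 4.01, and T0-adjusted analysis at a single visit has no consistent advantage over it. That stands. The SE gains above are measured against the same follow-up comparison unadjusted, not against group-by-time. What group-by-time does not supply is an estimated difference.

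Next, the t-test sentence is not limited to baseline. Given the two-mean sample size, it can naturally be read to include follow-up scores, and a t-test yields a difference whose interval is a matter of reporting. That also stands. The gap is that no visit is named, PSS-IBS is not tied to the test, no interval is promised and no adjustment is made.

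Three stronger readings are tempting and are not supported:
- That the trial will be judged on the diluted group main effect and is therefore underpowered. Nothing in section 12 indicates that this term would decide.
- That averaging T1 and T2 is also free. It chooses what is to be estimated. The documents do not say whether early, lasting or overall benefit is wanted, and the average loses to group-by-time once most of the effect has gone by T2.
- That the gain is as large as 29% or 35%. Those figures need r = 0.7 and ignore the entry rule.

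Finally, a change made now cannot restore prespecification if the results were already known. That is right, and it governs the label.

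**Conclusion.** The point holds as a free improvement of small to moderate size. The documents establish that T0 enters only as an outcome level, that no covariate is named, and that no difference, term or visit is tied to the primary indicator. They do not show the planned ANOVA to be invalid, since its group-by-time term is a sound test of treatment.

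T0 adjustment is the free part. The with-cut figures (2 / 6 / 14% at one visit, 3 / 8 / 18% for the T1-T2 mean) are the more relevant, because the protocol contains an entry cut. They rest on an assumed correlation and an assumed severity of the cut; the SEs and powers also assume that 5.15 and 4.01 apply to PSS-IBS. The averaged contrast is a reasonable summary but carries a condition: the effect must largely persist to T2.

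**What to change.** - Estimate the between-group PSS-IBS difference at T1 and at T2, each adjusted for T0, with 95% CIs. Use ANCOVA, or a mixed model with T1 and T2 as outcomes, T0 as covariate, and group, time and group-by-time terms. State which result decides effectiveness.
- Do the same for AAQ-II, SAQ and IBS-QOL, each with its own baseline.
- Keep the planned repeated-measures ANOVA alongside. Judge treatment in it by group-by-time, not by the time effect or by a group main effect that includes T0.
- If the T0-adjusted T1-T2 mean is given as a summary, always show both visits with it, so that a fading effect is visible.
- State when the change was made. Label it post hoc or a sensitivity analysis unless it was fixed before the data were seen.

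The cost is SAP wording and a re-run in the same software, with no new patients, visits or data.
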